**Table 1 – The Sepsis Screening Score**

This cutoff has a negative predictive value of 96%, which would rule out the majority patients without sepsis. Enrolled patients will be randomized only if they meet criteria for septic shock: 1) hypotension with MAP < 65 mmHg, and 2) evidence of hypoperfusion including lactic acid > 2.2 mmol/L, altered mental status, or decreased urine output of < 0.5 mL/kg in the past hour.

### Exclusion Criteria:

- Pregnancy
- Prisoners
- Non-survivable traumatic brain injury
- Evidence of ongoing hemorrhage (eg. active gastrointestinal bleed), history of congenital bleeding disorders, therapeutic anticoagulation
- History of congestive heart failure
- Major burns (>20% total body surface area)
- History of adverse reactions to blood product transfusion
- Contraindications to blood transfusions (eg. Jehovah's Witness)
- Contraindications to central venous line and arterial line placement
- Do-Not-Resuscitate or Comfort Care status
- Participation in another interventional study that specifically focuses on sepsis, involves the use of a non-approved product (medication or equipment), or interventions that affect blood coagulation.
- Pending transfer to another unit within the hospital that is not Shock Trauma Intensive Care Unit (STICU) or Medical Intensive Care Unit (MICU).

**Screening and Enrollment:** Patient screening and enrollment will take place at Memorial Hermann Hospital. The research team will screen patients by communicating with the on-call STICU and emergency department (ED) physicians daily to identify patients eligible for enrollment. Hospitalized medical patients on the floor who develop severe sepsis will be identified using the rapid response page, which is already in place to alert the rapid response team of medical floor patients with potential severe sepsis.

[figure not shown]
Enrolled patients will be monitored for up to 72 hours (in time for cultures to result) by the research team for development of septic shock (MAP  $\leq$  65 mmHg and evidence of poor perfusion, such as urine output  $< 0.5$  mL/kg/hr, venous lactic acid  $\geq 2.2$  mmol/L, altered mental status from baseline). Upon meeting these criteria for septic shock, patients will be randomized and immediately started on therapy fluid (either plasma or balanced crystalloids).

Crystalloid administration may already be underway prior to patient randomization. Receiving crystalloids prior to randomization *will not* be an exclusion criterion in this study as long as the total volume received has not met or exceeded 30 mL/kg. The research team will work expeditiously to obtain informed written consent, and once consent has been obtained and patient is randomized, prior fluids will be exchanged for therapy fluid (either plasma or balanced crystalloids).

#### **Informed Consent:**

Exception from Informed Consent will not be used in this trial. Written informed consent will be obtained from potential subjects or a legally authorized representative prior to randomization.

**Randomization:** Randomization will occur once the informed consent has been obtained. A 1:1 allocation will be used for the randomization. Subjects will be randomized to either the intervention arm (use of plasma) or the control arm (standard of care). Randomization will be performed using a computer-generated random sequence placed in opaque, consecutively-numbered, sealed envelopes kept in the locked Center for Translational Injury Research (CeTIR) office. A CeTIR research coordinator is available 24 hours a day, 7 days a week. Allocation will be 1:1. Patients will be stratified by enrollment location (STICU, ED, and Medical) in 5 blocks of 4 and 1 block of 6 for a total of 26 patients. **[Figure 4].**

**Figure 4** – Flow diagram depicting patient screening, enrollment, and randomization.

**Intervention:** Initial resuscitation with plasma will be 10 mL/kg (700 mL in a typical 70 kg adult). Traditional doses of plasma, when used to correct coagulopathy range from 10-15 mL/kg. The plasma will be administered at a rate of 2-3 mL/kg/hr (140-210 mL/hr in a typical 70 kg adult). A research physician will be at bedside to follow patient resuscitation. Plasma administration may be terminated before the entire dose is administered if patients show clinical improvement, or if the treating clinician has concerns about circulatory overload. After the initial dose of plasma has

been given, subsequent fluid resuscitation (crystalloid or colloid) will be given at the discretion of the treating clinician.

The blood bank will have thawed plasma available on call as soon as an eligible patient has been identified. Type and screen will be performed concurrently to provide donor-matched plasma for subjects randomized to intervention group. For patients who proceed to the operating room during fluid resuscitation, the anesthesiology team will continue fluid administration per study protocol.

**Control:** Usual care using balanced crystalloids (Iso-Lyte or Plasma-Lyte) only will follow Surviving Sepsis Campaign guidelines. Controls will receive 30 mL/kg (2100 mL in a typical 70 kg adult) of crystalloids within the first 3 hours. Crystalloid administration may be terminated before the entire dose has been administered if patients show clinical improvement, or if the treating clinician has concerns about circulatory overload. After the initial dose of crystalloids has been given, subsequent fluid resuscitation (crystalloid or colloid) will be given at the discretion of the treating clinician.

**Observational Arm:** Patients with suspected sepsis who do not meet the criteria for randomization or unable to obtain informed consent in a timely fashion (within 3 hours of research team being notified) will be enrolled in a prospective observational arm of the study. Baseline demographic and hospitalization data including the fluid therapy per the attending physician's discretion will be collected. Blood samples will also be collected at 0, 2, 3, 6, 12, and 24 hours upon determination of patients' eligibility for the observational study arm. A waiver of informed consent will be requested given that no intervention will be performed on the patient and that the study will be at minimal risk to the patient. The research team will attempt to obtain written informed consent from the patient or his/her legal authorized representative for 24 hours after patient enrollment into the observational study arm. If informed consent is denied by the patient or his/her legal authorized representative, no further data or blood samples will be collected and any data or blood samples collected prior to decline of participation will not be used in this study.

**Endpoints of Resuscitation:** Fluid resuscitation in both the intervention and the control arms will be titrated to serial reassessments of the patient's volume status via blood pressure monitoring (MAP > 65 mmHg), urine output measurements (goal of  $\geq 0.5$  cc/kg/hr), CVP measurements (>8 mmHg), stroke-volume variation on hemodynamic monitors (such as the Vigileo), inferior vena cava (IVC) collapsibility index via bedside ultrasound, and lactate clearance (goal of  $\geq 50\%$  clearance after 6 hours of resuscitation). Serial laboratory examinations including lactate levels will be performed per standard of care in the ICU, until the lactate has normalized. Additional fluid support after the initial plasma or crystalloid bolus will be given at the discretion of the treating clinician, keeping in mind that septic shock patients in several randomized trials required 6-8L crystalloid per day.

**Co-interventions:** Both groups will receive standard care following Surviving Sepsis Guidelines, including procurement of blood cultures, administration of broad-spectrum antibiotics, transfusion of packed red blood cells for hemoglobin < 7 mg/dL, and use of vasopressors to maintain MAP > 65 mmHg.

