### **Study Design & Methods:**

The proposed trial is a pilot, efficacy, single-center RCT comparing initial plasma to balanced crystalloid resuscitation in surgical patients with septic shock. The trial will investigate modulation of SHINE as a strategy by which outcomes in shock patients may be improved. The trial will follow the Consolidated Standards in Reporting of Trials (CONSORT) guidelines and has been registered on ClinicalTrials.gov (NCT03366220).

**Setting:** The study will take place at Memorial Hermann Hospital – Texas Medical Center (MHH-TMC), a Level I trauma and tertiary care center located in Houston, Texas.

**Study population:** The target population includes critically ill (including medical patients), traumatically-injured or surgical patients who have sepsis, hypotension with MAP < 65 mmHg, and signs of hypoperfusion such as lactic acid > 2.2 mmol/L, altered mental status or decreased urine output (< 0.5 mL/kg in the past hour).

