#### **Data Collection:**

Data collected will include: demographics, past medical history, hospital information including

initial resuscitation information and post-operative care, complications (**Appendix A**), and discharge information. A list of the data elements to be collected can be found in Appendix A. Data will be collected from the subject's medical record and the trauma registry. Risk/Safety evaluation will be performed at half enrollment (at 13 enrolled and randomized patients).

All subjects enrolled in this study will be assigned a study specific number. The de-identified data will be entered into a secure, password protected database accessible to only those involved in the study. A study linking log which will link subject identifiers to the study number will be kept by the study PI.

To ensure patient confidentiality is maintained at all times, all data will be maintained in accordance with HIPAA rules and regulations. Hard copy source documentation will be kept in a secure area in a locked office and electronic data will be stored on secure, password-protected computers accessible to only those study specific personnel.

**Outcomes - Biomarkers of Endothelial and Glycocalyx Injury:** The primary outcome is a reduction in serum biomarkers associated with glycocalyx breakdown (syndecan-1, sTM), endothelial leakage (sFLT-1, VEGF, sTM), sympatho-adrenal activation (NE, epinephrine), and inflammation (VEGF, sRAGE, HMGB-1, IL-6, 8, 10, 1 $\alpha$ , 1 $\beta$ ) in the plasma group. A rodent model has shown evidence of glycocalyx restoration after 2 hours of resuscitation with plasma as compared to crystalloid. Biomarkers will be drawn at 0, 2, end of initial bolus of fluid administration, 6, 12, and 24 hours to evaluate their trend in response to plasma versus crystalloid resuscitation. Timing of biomarker lab draw at the end of the initial fluid bolus will be variable since termination of fluid resuscitation depends on patients' clinical response. Lactic acid will be drawn per standard of care to guide resuscitation. Standard labs for critically ill patients (such as complete blood count, basic metabolic panel, and arterial blood gases) will be obtained per STICU protocol. See **Table 2** for timing of biomarker lab draws. Funding for measuring biomarkers will be obtained from an additional source if the grant is awarded.

Table 2: Timing of Lab Draws Upon Randomization (T=0) in hours						

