	T = 0	T = 2	T = EoR	T = 6	T = 12	T = 24
Serum Biomarkers	✓	✓	✓	✓	✓	✓

Serum biomarkers = syndecan-1, sTM, sFLT-1, VEGF, sRAGE, HMGB-1, IL-6, 8, 10, 1 $\alpha$ , 1 $\beta$ , vWF, tPA, NE, and epinephrine;  
EoR = End of Resuscitation (variable, depending on patient response to fluids)

resuscitation, time on vasopressors, time until lactate normalization, ventilator days, ICU-free days, and hospital length of stay. Organ dysfunction will be measured including acute lung injury and acute renal failure. Standardized definitions will be used as outlined in the method of operation used in previously conducted trials by our group. Potential harms of plasma administration will be assessed including symptomatic and asymptomatic venous thromboembolisms, transfusion-related allergic reactions, febrile non-hemolytic transfusion reaction, delayed-serological transfusion reactions, and transfusion-associated circulatory overload. Risk/safety evaluation will be performed at half recruitment (13 randomized patients).

**Blinding:** The healthcare provider will not be able to be blinded to the study intervention. The outcome assessors will be blinded when feasible, and the laboratory technicians and statisticians will be blinded.

**Sample Size:** We propose to enroll 26 patients (13 in each treatment arm) for the pilot randomized study to obtain unbiased estimates of treatment effect. We propose to enroll up to 100 patients to the observational study arm. Because this is a feasibility pilot study, we do not provide a power analysis for any outcomes since no formal hypothesis testing will be conducted. Instead, we will calculate estimates of treatment effect and 95% confidence intervals for all measures. We will also calculate probabilities of treatment benefit/harm using Bayesian analyses and conservative neutral priors. These estimates will inform the design of a future larger trial.

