**Statistical Analysis:** Because this is a pilot, efficacy trial, we will perform both a per-protocol and an intention-to-treat analysis. Both frequentist and Bayesian analysis will be performed. For the primary outcome and all continuous outcomes (using variable transformations if needed), we will use mixed models that include group and time period as covariates with a random subject effect. We will report group differences and 95% CIs from these models. For binary outcomes, a log binomial (or Poisson in case of non-convergence) will be used to estimate relative risks and 95% CIs. Hazard ratios and 95% CIs will be reported for time-to-event comparisons. For the Bayesian analysis, neutral conservative priors (that exclude large treatment effects almost never seen with medical interventions) will be used to estimate the probability of both benefits and harms, as defined by our primary and secondary outcomes.

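### Randomisation is stratified by enrollment location, but the mixed model for the primary and continuous outcomes leaves location out, so the 95% CI for the overall group difference is probably too wide

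*Combined protocol and SAP*

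**What the plan says.** The Randomization paragraph (under Informed Consent) names one stratification factor with three levels: "Patients will be stratified by enrollment location (STICU, ED, and Medical"). It gives the block structure as "in 5 blocks of 4 and 1 block of 6 for a total of 26 patients". It does not say how the six blocks are divided among the three locations.

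The Statistical Analysis paragraph specifies, for the primary outcome and all continuous outcomes, "mixed models that include group and time period as covariates with a random subject effect". It continues: "We will report group differences and 95% CIs from these models". Location is not listed there or added elsewhere, and neither is a group-by-time term. The reference distribution for the interval (t or normal) is not stated.

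The Sample Size paragraph explains that there is no power analysis because no formal testing is planned. Instead, "we will calculate estimates of treatment effect and 95% confidence intervals for all measures". These estimates are meant to inform a larger trial.

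**The concern.** Balancing the arms within location removes between-location variance from the sampling error of the group difference. A model without location does not know this. It leaves that variance in the random subject effect, and so overstates the standard error of the difference.

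Location may well be prognostic. The Study population paragraph describes "critically ill (including medical patients), traumatically-injured or surgical patients who have sepsis", and location is the only factor the sponsor chose to stratify on.

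The interval is a main output of this pilot, because testing and power are set aside. An interval that is too wide gives away precision that stratification has already bought, in a trial of only 26 patients. For scale, a CI 10% too wide is like using 1/1.10² = 0.83 of the sample, a loss of about one sixth.

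**Working it through.** **The plan's own figure.** 5 × 4 + 1 × 6 = 26 = 2 × 13, which matches the stated total and 13 per arm. The plan gives no power or CI-width figure to reproduce.

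**Inputs from the protocol.** N = 26, 1:1 allocation, three locations, six draws (0, 2, end of bolus, 6, 12 and 24 hours), and a model with group, time and random subject.

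**Assumed inputs.** ICC of 0.3, 0.5 or 0.7 for repeated draws within a patient. R², the share of between-patient variance explained by location, from 0 to 0.30. Data are taken as complete.

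**Reduction to subject means.** With complete data, the group effect in the random-subject model equals an analysis of 26 subject means. Setting the total variance of one draw to 1, the variance of a subject mean is:

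- location in the error: ICC + (1 − ICC)/6
- location removed: ICC(1 − R²) + (1 − ICC)/6

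The residual degrees of freedom are 24 without location and 22 with it, so t₂₄ = 2.0639 and t₂₂ = 2.0739.

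**Width ratio, blocks within location, t reference.**

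Ratio (without / with location) = t₂₄ √[ICC + (1 − ICC)/6] / { t₂₂ √[ICC(1 − R²) + (1 − ICC)/6] }

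Example, ICC 0.5 and R² 0.10: √(0.5833/0.5333) = 1.0458, and 1.0458 × 2.0639/2.0739 = 1.041.

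This simple form is slightly low. In a sample of 26 the unadjusted mean square picks up the location variance multiplied by N/(N − 2) = 26/24. The refined ratio is (t₂₄/t₂₂) √[1 + (26/24) × f/(1 − f)], where f = ICC·R² / [ICC + (1 − ICC)/6] is location's share of the variance of subject means. Example, ICC 0.5 and R² 0.30: f = 0.15/0.5833 = 0.257, giving 1.167.

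| R² | Simple ratio (ICC 0.3 / 0.5 / 0.7) | Refined ratio (ICC 0.3 / 0.5 / 0.7) |
|---|---|---|
| 0 | 0.995 / 0.995 / 0.995 | 0.995 / 0.995 / 0.995 |
| 0.05 | 1.014 / 1.017 / 1.019 | 1.015 / 1.019 / 1.021 |
| 0.10 | 1.033 / 1.041 / 1.045 | 1.036 / 1.045 / 1.049 |
| 0.20 | 1.076 / 1.093 / 1.103 | 1.082 / 1.101 / 1.112 |
| 0.30 | 1.124 / 1.155 / 1.173 | 1.134 / 1.167 / 1.186 |

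**Simulation** (6,000 trials per setting, N = 26, ICC 0.3 to 0.7). Two nested layouts were run: blocks of 4 within location with even accrual, and whole blocks filling 8/8/10.

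| R² | Width ratio | Coverage without location, t reference |
|---|---|---|
| 0 | 0.992-0.997 | nominal |
| 0.10 | 1.032-1.052 | 95.5-96.0% |
| 0.20 | not tabulated | 96.6-97.1% |
| 0.30 | 1.127-1.194 | 96.9-97.9% |

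With location in the model and a t reference, coverage is 94.6-95.5%. A separate simulation with 20,000 trials per setting, indexed by f instead of R², gave the same pattern. Its unadjusted coverage was 96.1-96.3% at f = 0.10 for complete-block and random-size layouts, and 97.8-98.3% at f = 0.30.

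**Normal reference, nested blocks.** Coverage without location is 94.6-95.2% at R² = 0.10 and 96.1-97.3% at 0.30. Coverage with location is only 93.2-94.3%.

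**Single list of 5 × 4 + 6, not nested, t reference.** Coverage without location is 94.6-95.3% for R² from 0 to 0.30. The width ratio is 0.951-0.953 at R² = 0, 0.989-1.001 at 0.10 and 1.076-1.124 at 0.30. Here adjustment changes precision only.

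**Change over time.** A constant location effect cancels from within-patient contrasts, so these are unaffected.

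**The case against.** The case against is that the harm is conditional and small.

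- **Nesting is not settled.** The six blocks sum exactly to the trial size and no location quotas are given, which fits a single list as well as three. Under one list there is no coverage error, and adjusting would widen the CI by about 5% if location explained nothing. This stands as a condition. The word used is stratified, which ordinarily means blocks within stratum, but the sponsor should confirm it. The flow diagram cited there is not visible in the text reviewed and may settle it.
- **The primary question may be about change.** The outcomes section describes the draws as intended "to evaluate their trend in response to plasma versus crystalloid resuscitation", and change contrasts are untouched. This also stands. However, the model as written lists no group-by-time term, so the effect it estimates is the overall group difference.
- **The size is assumed.** All randomised patients must be in septic shock, so a 20-30% location share may be high. At 10% or less the excess is small.
- **Adding location alone can lower coverage.** With a normal reference this is correct, which is why the change must be paired with a t reference.
- **No decision hangs on the interval.** The error is conservative, and this is a pilot without testing. That limits the severity. But estimates with intervals are what the pilot offers in place of tests, so their calibration still matters.

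**Conclusion.** The concern holds. Location is used to randomise and is absent from the mixed model. Given nested blocks, a prognostic location and a t reference, the 95% CI for the overall group difference is too wide: by about 1-2% if location explains 5% of between-patient variance, 3-5% at 10%, 8-11% at 20% and 12-19% at 30%. These figures assume ICC 0.3 to 0.7, six draws per patient and complete data; the documents supply neither the ICC nor the location effect. The point estimate is not biased.

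The change should be made, but it is not critical to the trial's validity. Confidence is medium, because the documents do not settle the three conditions. The binary and time-to-event models were not assessed.

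**What to change.** In the Statistical Analysis paragraph, add the location stratum used at randomisation as a fixed effect in the mixed models for the primary and continuous outcomes, in both the frequentist and Bayesian versions. State a t reference for the frequentist intervals, for example with Kenward-Roger or Satterthwaite degrees of freedom. In the Randomization paragraph, confirm that blocks are run within location and say how they are divided. Leave the binary and time-to-event models as planned.

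The cost is one analysis sentence, the clarification on blocks, and 2 degrees of freedom. If location turns out not to be prognostic, adjusting widens the CI by:

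- about 0.5-0.9% with nested blocks and even accrual;
- about 1.1-1.5% with nested blocks and uneven accrual (50/30/20 or 60/30/10 across locations);
- about 5% if the blocks are not nested.

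### Block sizes printed in the protocol of a trial with unblinded staff make about 15% to 31% of allocations certain in advance, despite sealed envelopes

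*Combined protocol and SAP*

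**What the plan says.** The Randomization paragraph (under Informed Consent) gives the whole block structure: "in 5 blocks of 4 and 1 block of 6 for a total of 26 patients". On the ratio it says "A 1:1 allocation will be used for the randomization", and on strata "Patients will be stratified by enrollment location (STICU, ED, and Medical". Concealment rests on "opaque, consecutively-numbered, sealed envelopes kept in the locked Center for Translational Injury Research (CeTIR) office". It does not say how the six blocks are divided among the three locations, where the block of 6 falls, who generates the list, or whether recruiting staff are kept unaware of the block sizes.

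The Blinding paragraph states "The healthcare provider will not be able to be blinded to the study intervention". It then adds "The outcome assessors will be blinded when feasible, and the laboratory technicians and statisticians will be blinded". None of the blinded roles is a recruiting role.

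The research team's part is described in several places. Under Screening and Enrollment it screens daily and works to obtain consent, and "Enrolled patients will be monitored for up to 72 hours (in time for cultures to result) by the research team for development of septic shock". Under Intervention, a research physician attends at the bedside. Under Observational Arm, a patient whose consent cannot be obtained within 3 hours of the team being notified goes to the observational arm instead.

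**The concern.** Sealed envelopes stop staff from reading the next card. They do not stop staff from counting. In a balanced block of known size, once one arm has used its places, every allocation left in that block is determined. Before that point, the arm used less so far is the better bet. With one centre, 26 patients and visible treatment, past allocations are easy to follow. The strata are locations that recruiters know, so they can keep the count separately for each.

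Foreknowledge matters only if someone can act on it. Here there is some room to do so:

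- when a patient is approached and how consent is timed;
- the judgement of altered mental status, one of the signs of hypoperfusion;
- the 3-hour consent limit, which gives a patient who is not randomized another place in the study.

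At stake is the comparability of the arms at entry. The Sample Size paragraph justifies the trial by unbiased estimates of treatment effect that will inform a larger trial. With 13 per arm, one patient is 1/13 = 7.7% of an arm. The mixed models in Statistical Analysis name only group and time period as covariates, so they list no baseline characteristics with which to offset selective entry.

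**Working it through.** **Inputs.** From Randomization: five blocks of 4, one block of 6, 1:1, three strata. From Sample Size: "We propose to enroll 26 patients (13 in each treatment arm) for the pilot randomized study". Assumption: each block is balanced (2+2 or 3+3), as 1:1 permuted blocks normally are.

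**The plan's own figure.** 5 × 4 + 1 × 6 = 26, which agrees with the stated sample size.

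**Certain allocations, boundaries known and blocks filled.** Count the places left in a block after one arm is exhausted.

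- Block of 4: 6 sequences. Two leave 2 certain places and four leave 1. Mean = (2×2 + 4×1)/6 = 8/6 = 1.333.
- Block of 6: 20 sequences. Two leave 3, six leave 2 and twelve leave 1. Mean = (2×3 + 6×2 + 12×1)/20 = 30/20 = 1.5.
- Both agree with the general formula 2m/(m+1) for a block of size 2m: 4/3 for m = 2 and 6/4 for m = 3.
- Total = 5 × 1.333 + 1.5 = 8.17, and 8.17/26 = 31.4%.
- This is an expectation. The realised number can run from 6 (5×1 + 1) to 13 (5×2 + 3) of 26, that is 23% to 50%.

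**Best guess, same conditions.** Always guess the arm with more places left, and add the chance of being right at each position.

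- Block of 4: 1/2 + 2/3 + 2/3 + 1 = 2.833.
- Block of 6: 0.5 + 0.6 + 0.6 + 0.7 + 0.7 + 1 = 4.1.
- Total = 5 × 2.833 + 4.1 = 18.27, and 18.27/26 = 70.3%. Chance alone gives 13/26 = 50%.

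**Position of the block of 6 unknown.** The protocol gives the mix of blocks but not their order. An observer was simulated who knows the mix, gives the six possible positions equal weight, and updates by Bayes' rule after each allocation. An allocation counts as certain only if every position still possible gives the same answer. There were 3,000 runs for each layout.

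- Single list: about 3.9/26 = 15% certain; best guess right 70%.
- Two blocks in each of three strata (an assumed split): about 4.3/26 = 17% certain; best guess right about 71%.

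Hiding the position roughly halves the certain allocations, because an apparently exhausted block of 4 might be the block of 6. It leaves the best guess almost unchanged.

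**Blocks left unfilled.** With known blocks of 4, patients arriving at random in three strata and recruitment stopping at 26 (20,000 runs), about 7.4/26 = 28% are certain. The result is the same to the nearest percent for equal strata and for an assumed 60/25/15 split.

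**After the fix.** With block sizes drawn at random from 4/6, 2/4/6 or 2/4 (assumed options), three equally busy strata, and an observer who knows which sizes are possible, certain allocations fall to about 3% to 9%. The best guess is still right about 67% to 70% of the time.

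**The case against.** The other side has four good arguments.

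- **The 31% is conditional.** A reader might infer that 31% of allocations can simply be known in advance. That needs staff to know every boundary, including the stratum and position of the block of 6, and needs all blocks to fill. The protocol states neither. This stands, so the figure is given as a range with its conditions. The best-guess rate of about 70% does not depend on knowing where the block of 6 is.
- **The team does not freely choose the moment.** A reader might infer that it decides when to randomize. Screening and Enrollment instead has randomization follow once the shock criteria are met, and mean arterial pressure, lactate and urine output are measured. That reading is therefore too strong. Some discretion remains in approach, consent and the judgement of mental status. How far that judgement reaches is unclear. The list under Inclusion Criteria lets any one sign suffice, while the text below Table 1 and Screening and Enrollment require hypotension together with hypoperfusion. Those passages must be reconciled.
- **Steering is awkward.** Shock may develop up to 72 hours after enrollment, so the allocation foreseen at approach may not be the one in force at the trigger. This stands for such patients. It does not help for those who already meet the criteria when consent is obtained.
- **Predictability is not bias.** This is a pilot without formal hypothesis testing, and biomarkers are drawn at T = 0, so an imbalance in the primary markers would be visible. This also stands, but seeing an imbalance does not prevent it, and unmeasured differences would stay hidden.

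The documents also do not show what recruiters know. That they have read the protocol's block sizes is a reasonable inference, not a documented fact.

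**Conclusion.** The concern holds in limited form. With block sizes printed in the protocol, treatment visible and one team handling recruitment and monitoring, sealed envelopes do not fully conceal the next allocation. The range for certain allocations runs from about 15% (single list, position of the block of 6 unknown) to 31% (all boundaries known, all blocks filled). These figures assume balanced blocks and an observer who tracks every past allocation, by location where lists are separate.

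A reader might go further and infer that the estimates are biased or that entry was steered. The documents support neither: no selective entry is shown, and no bias in any outcome has been calculated. What they show is an avoidable route to selective entry in a trial that is too small to absorb much of it. This is a cheap improvement that should be made, not a flaw that invalidates the design.

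**What to change.** - Have someone outside the recruiting team generate the list, with block sizes varying at random within each location stratum.
- Remove the block sizes and counts from the protocol. State only that permuted blocks of varying, undisclosed size are used, stratified by location. Keep the sizes, their order and their division among locations in a restricted file until the last patient is randomized.
- Record the time at which the shock criteria were met before the envelope is opened, so that any gap between eligibility and randomization can be audited.

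The cost is a new computer-generated list, a short amendment and one extra time field. The arms may end a patient or so away from 13:13, which matters little where only estimates and intervals are planned. The gain is mainly in certain allocations; the best-guess rate falls only a little, so the time record is worth having alongside the new list.
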